I have read this protocol. I approve this document and I agree that it contains all necessary details for carrying out the study as described. I will conduct this study in accordance with the design and specific provision of this protocol and will make a reasonable effort to complete the study within the time designated. I will provide copies of this protocol and access to all information furnished by Aldeyra Therapeutics, Inc. to study personnel under my supervision. I will discuss this material with them to ensure they are fully informed about the study product and study procedures. I will let them know that this information is confidential and proprietary to Aldeyra Therapeutics, Inc. and that it may not be further disclosed to third parties. I understand that the study may be terminated or enrollment suspended at any time by Aldeyra Therapeutics, Inc., with or without cause, or by me if it becomes necessary to protect the best interests of the study subjects.

I agree to conduct this study in full accordance with Food and Drug Administration Regulations, Institutional Review Board/Ethic Committee Regulations, and International Council for Harmonisation Guidelines for Good Clinical Practices.

Investigator's Signature

Date

Investigator's Printed Name

SYNOPSIS

TITLE: A Double-Blind Phase 1b Study to Assess the Interaction Between ADX-629 and Ethanol While Exploring the Safety, Tolerability, and Activity of ADX-629 in Subjects With Elevated Ethanol Levels

PROTOCOL NUMBER: ADX-629-ET-001

INVESTIGATIONAL PRODUCT: ADX-629

PHASE: 1b

INDICATION: Elevated ethanol levels

OBJECTIVE:

The primary objective is to assess the interaction between ADX-629 and ethanol while exploring the safety, tolerability, and activity of ADX-629 in subjects with elevated ethanol levels.

POPULATION:

Inclusion Criteria:

Subjects meeting all of the following criteria will be considered eligible for the study:

1. Male or female subjects between the ages of 21 and 65 years, inclusive, at Screening;
2. [REDACTED]
3. Subjects with the ability to obtain transportation to and from the study site;
4. Subjects with a history of alcohol-related symptoms or negative symptomatology following the consumption of ≤ 4 alcoholic beverages;

Note: Alcohol-related symptoms may include any of the following: headache, flushing, fatigue, diarrhea, nausea, dizziness, confusion/disorientation, or nystagmus.

5. [REDACTED]
6. Subjects who agree to avoid use of prescription or over-the-counter medications, including topicals, herbal supplements, dietary supplements (excluding fish oil), or nutraceuticals within 14 days prior to Screening until the end of the study;

Note: Subjects must avoid oral contraceptives from within 7 days prior to Screening until the end of the study and immunomodulators (eg, corticosteroids, cytokine inhibitors, and Janus kinase inhibitors) from within 60 days prior to Screening until the end of the study.

7. Subjects (all females of childbearing potential [FCBPs] and males with a female partner of childbearing potential) who agree to use an effective form of contraception (nonhormonal or barrier method) during the study and for 7 days after the last dose of study drug;

Note: An FCBP is defined as any female, regardless of sexual orientation, who has not undergone a hysterectomy, bilateral oophorectomy, salpingectomy, or bilateral tubal ligation or has not been naturally postmenopausal for at least 12 consecutive months (ie, has had menses at any time in the preceding 12 consecutive months) with a negative follicle-stimulating hormone (FSH) test. An FSH test will be performed at Screening in all naturally postmenopausal women to confirm menopausal status.

Note: Sperm donation is also prohibited during the study and for 90 days after the last dose of study drug.

8. Subjects who are willing to consume the standardized alcohol preparation;

9. [REDACTED]

10. Subjects who agree to abstain from consumption of non-study alcohol during the study.

Exclusion Criteria:

Subjects meeting any of the following criteria will be excluded from the study:

1. [REDACTED]

2. Subjects with abnormal laboratory values of clinical significance, at the discretion of the Investigator, at Screening;

Note: 1 repeat of laboratory assessments is allowed to confirm abnormal values.

3. [REDACTED]

4. Subjects with a history of or active:

- Reactive airway disease;
- Diabetes;
- Kidney or bladder stones;
- Kidney disease (including past or current dialysis requirement);
- Liver disease;
- Stomach ulcer;
- Organ transplant;
- Gastric bypass; or
- Any other medical/surgical condition of clinical significance, at the discretion of the Investigator.

5. Subjects with nicotine product use within 14 days prior to Screening until the end of the study;

6. Subjects with any history of or current alcohol or other substance use disorder diagnosed according to the Diagnostic and Statistical Manual of Mental Disorders Fifth Edition;
7. Subjects with a positive urine drug screen or breath alcohol test at Screening or Check-In (both treatment periods);
8. [REDACTED]
9. Subjects who are currently pregnant or lactating or plan to become pregnant during the study;
Note: A serum pregnancy test will be performed in all FCBPs at Screening and a urine pregnancy test will be performed at Check-In (both treatment periods).
10. Subjects who are positive for HIV antibody, hepatitis C virus antibody, hepatitis B virus surface antigen, or severe acute respiratory syndrome coronavirus-2 RNA;
11. Subjects who have participated in any other investigational study within the past 30 days or within 5 half-lives of the investigational therapy, whichever is longer, at Screening;
12. Subjects currently taking or who cannot abstain from corticosteroids, cytokine inhibitors, Janus kinase inhibitors, and/or nonsteroidal anti-inflammatory drugs; or
13. Subjects currently taking or who cannot abstain from medications that can cause a disulfiram-like reaction (eg, metronidazole) or who have taken such medications within the past 30 days at Screening.

STUDY DESIGN AND DURATION:

ADX-629-ET-001 is a Phase 1b, single-center, double-blind, placebo-controlled, randomized, crossover study to assess the interaction between ADX-629 and ethanol while exploring the safety, tolerability, and activity of ADX-629 in subjects with elevated ethanol levels. Approximately 30 subjects are expected to be enrolled in the study.

This study will utilize a 2-sequence, 2-period, 2-way crossover design. Subjects will be randomized to 1 of 2 treatment sequences (AB or BA) on Day 1 of Treatment Period 1.

- Treatment A: 3 oral doses of ADX-629 600 mg (2 × 300 mg) oral tablets; and
- Treatment B: 3 oral doses of matching placebo.

Study procedures will be completed during the following periods:

- A Screening Period (Day -28 to -2);
- Two 3-day inpatient periods (Treatment Periods 1 and 2) (from Check-In through completion of treatment period), each consisting of the following:
 - Check-In: Subjects will be admitted to the study site on the day prior to dosing in each treatment period. Baseline symptom and sign assessments (except for the Clinical Global Impression [CGI]-Improvement Scale) will be completed, and subjects will then be housed overnight where they will be required to adhere to a standardized high-fat, high-sucrose diet;

Note: Subjects will be reminded at the beginning of each treatment period that this study is placebo-controlled. The placebo-control reminder text will be read as follows: "You

are participating in a placebo-controlled study, which means that you will not know if you are taking a sugar pill or a drug pill. It is important that you try not to decide whether you have taken a sugar pill or a drug pill. Any questions that you answer about how you are feeling should not be influenced by whether or not you believe you have taken a sugar pill or a drug pill. Please answer questions about how you are feeling as if you had not taken any pill at all.”

- Day 1: 1 dose of study drug will be administered at approximately 4:30 pm followed by standardized ethanol consumption as outlined in the manual, and then 1 dose of study drug will be administered at approximately 7 pm followed by continued standardized ethanol consumption to reach a target blood alcohol concentration (BAC) of 0.14 g/100 mL, measured via breathalyzer. For more details on the breathalyzer measurements, refer to the Study Procedures Manual. Symptom and sign assessments (with the exception of the CGI-Improvement Scale) will be evaluated and should be completed as soon as practical after target BAC is reached. Study procedures will be reviewed for randomized subjects, and, based on the emerging data, the standardized ethanol solution and/or BAC testing methods may be modified as needed to ensure target BAC is reached within a 4-hour window for the remaining subjects; and

Note: Subjects will be observed for safety during the treatment periods by study site personnel who will be present to assist subjects at all times; there will be a minimum requirement of at least 2 study site personnel to assist subjects during their assessments. Safety measures will be in place to prevent falling.

Note: Ethanol will be administered in a standardized oral solution. For more details on the consumption guidelines, refer to the Study Procedures Manual.

- Day 2: 1 dose of study drug will be administered at approximately 8 am, and symptom and sign assessments (including the CGI-Improvement Scale) will be completed at approximately 7 am, 10 am, and 1 pm. Subjects will be discharged from the study site after completion of study procedures (approximately 12 hours after the last dose of study drug). Prior to discharge, vital signs will be measured. Subjects will have to achieve a BAC of 0.00 g/100 mL as measured by a breathalyzer before discharge.
- A follow-up telephone call will occur 3 days (± 1 day) after completion of Treatment Period 2.

For subjects who are withdrawn from the study prior to completion, study procedures will be performed at an Early Termination Visit.

There will be at least a 14-day washout period between the last dose of study drug in Treatment Period 1 and the first dose of study drug in Treatment Period 2. Subjects will need to refrain from drinking alcohol during the washout period.

An individual subject's participation in the study is estimated to be approximately 41 days.

DOSAGE FORMS AND ROUTE OF ADMINISTRATION:

Aldeyra Therapeutics, Inc. will supply sufficient quantities of study drug (ADX-629 and matching placebo) to allow for completion of the study. The lot numbers will be recorded in the final Clinical Study Report.

ENDPOINTS:

The study is not formally powered and all endpoints are exploratory in nature.

The primary exploratory efficacy endpoints include the following:

- Assessment of symptoms using the Global Impression Visual Analog Scale, CGI-Impairment Severity Scale, CGI-Improvement Scale, and the Alcohol Toxicity Symptom Scale;
- Assessment of signs, determined by evaluation of the following:
 - Objective flushing and ocular redness scales (via digital photography); and
 - Proprioception tests (Romberg Test [time of up to 60 seconds], One Leg Stand Test [time of up to 60 seconds], Straight-Line Heel-to-Toe Test [up to 100 steps]).
- Assessment of ADX-629 activity, determined by evaluation of the following pharmacodynamic (PD) markers, for both treatment periods, on Day 1 pre-dose, on Day 1 one hour after the target BAC is achieved, and on Day 2 one hour after the last dose of study drug:
 - 4-hydroxynonenal (HNE), acetaldehyde, malondialdehyde-acetaldehyde adduct (MAA), and malondialdehyde (MDA) plasma concentrations; and
 - Plasma cytokine concentrations including, but not limited to, interferon gamma, interleukin (IL)-1b, IL-10, IL-12, and IL-17.

The primary safety endpoint is the safety and tolerability of ADX-629, determined by evaluation of the following:

- Adverse events;
- Physical examinations;
- Vital signs (blood pressure, heart rate, respiratory rate, temperature, and oxygen saturation);
- 12-lead electrocardiograms;
- BAC;
- Clinical laboratory assessments (including chemistry, hematology, and urinalysis); and
- Lipid panel evaluations.

STATISTICAL ANALYSES:

The Safety Population is defined as all randomized subjects who receive at least 1 dose of study drug.

The PD Population is defined as all subjects who have at least 1 PD measurement.

In general, categorical variables will be summarized by the count and percentage of subjects. Continuous variables will be summarized by the number of non-missing observations, mean, standard deviation, median, minimum, and maximum values.

In general, the comparison of change from baseline in endpoints over time between the 2 treatment sequences will be assessed by a mixed effect model for repeated measures. The model will include change from baseline as the dependent variable with sequence, period, timepoint, treatment, and the interaction of treatment by timepoint as fixed effects, and baseline as a covariate.

Efficacy data will also be listed and summarized descriptively.

Demographic and baseline data will be listed and summarized descriptively.

Safety and tolerability assessments will be listed and summarized descriptively as the observations and, when appropriate, as the change from baseline, and shift tables will be produced.

The statistical analyses to be performed will be further outlined in the Statistical Analysis Plan (SAP). The SAP will supersede the protocol if there are any differences between the 2 documents in the plans for data analysis, and these differences will be noted in the SAP.

SAMPLE SIZE DETERMINATION:

Approximately 30 subjects are expected to be enrolled in the study. The sample size is not based on statistical considerations and is not formally powered as all endpoints are exploratory in nature.

SITES: 1 study site in the United States

SPONSOR:

Aldeyra Therapeutics, Inc.
[name]
[name]
United States
[contact]
[contact]

TABLE OF CONTENTS

Signature Page	2
Investigator Agreement.....	3
Synopsis	4
Table of Contents.....	10
List of Abbreviations and Definition of Terms.....	13
1 Introduction and Background Information	15
1.1 Background	15
1.1.1 Nonclinical Studies of ADX-629	16

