- Day 1: 1 dose of study drug will be administered at approximately 4:30 pm followed by standardized ethanol consumption as outlined in the manual, and then 1 dose of study drug will be administered at approximately 7 pm followed by continued standardized ethanol consumption to reach a target blood alcohol concentration (BAC) of 0.14 g/100 mL, measured via breathalyzer. For more details on the breathalyzer measurements, refer to the Study Procedures Manual. Symptom and sign assessments (with the exception of the CGI-Improvement Scale) will be evaluated and should be completed as soon as practical after target BAC is reached. Study procedures will be reviewed for randomized subjects, and, based on the emerging data, the standardized ethanol solution and/or BAC testing methods may be modified as needed to ensure target BAC is reached within a 4-hour window for the remaining subjects; and

Note: Subjects will be observed for safety during the treatment periods by study site personnel who will be present to assist subjects at all times; there will be a minimum

requirement of at least 2 study site personnel to assist subjects during their assessments. Safety measures will be in place to prevent falling.

Note: Ethanol will be administered in a standardized oral solution. For more details on the consumption guidelines, refer to the Study Procedures Manual.

- Day 2: 1 dose of study drug will be administered at approximately 8 am, and symptom and sign assessments (including the CGI-Improvement Scale) will be completed at approximately 7 am, 10 am, and 1 pm. Subjects will be discharged from the study site after completion of study procedures (approximately 12 hours after the last dose of study drug). Prior to discharge, vital signs will be measured. Subjects will have to achieve a BAC of 0.00 g/100 mL as measured by a breathalyzer before discharge.
- A follow-up telephone call will occur 3 days (± 1 day) after completion of Treatment Period 2.

For subjects who are withdrawn from the study prior to completion, study procedures will be performed at an Early Termination Visit.

There will be at least a 14-day washout period between the last dose of study drug in Treatment Period 1 and the first dose of study drug in Treatment Period 2. Subjects will need to refrain from drinking alcohol during the washout period.

An individual subject's participation in the study is estimated to be approximately 41 days.

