5 STUDY TREATMENTS

5.1 Treatment Groups

All subjects will receive 3 doses of ADX-629 600 mg (2×300 mg) oral tablets and 3 doses of matching placebo. The study drug will be administered twice on Day 1, the first dose prior to the commencement of the standardized ethanol consumption, and once on the day following ethanol consumption (Day 2).

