9.2.5 Sample Size Determination

Approximately 30 subjects are expected to be enrolled in the study. The sample size is not based on statistical considerations and is not formally powered as all endpoints are exploratory in nature.

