2.2 Study Design

2.2.1 *Overview*

ADX-629-ET-001 is a Phase 1b, single-center, double-blind, placebo-controlled, randomized, crossover study to assess the interaction between ADX-629 and ethanol while exploring the safety, tolerability, and activity of ADX-629 in subjects with elevated ethanol levels. Approximately 30 subjects are expected to be enrolled in the study.

This study will utilize a 2-sequence, 2-period, 2-way crossover design. Subjects will be randomized to 1 of 2 treatment sequences (AB or BA) on Day 1 of Treatment Period 1.

- Treatment A: 3 oral doses of ADX-629 600 mg (2 × 300 mg) oral tablets; and
- Treatment B: 3 oral doses of matching placebo.

Study procedures will be completed during the following periods:

- A Screening Period (Day -28 to -2);
- Two 3-day inpatient periods (Treatment Periods 1 and 2) (from Check-In through completion of treatment period), each consisting of the following:
 - Check-In: Subjects will be admitted to the study site on the day prior to dosing in each treatment period. Baseline symptom and sign assessments (except for the Clinical Global Impression [CGI] Improvement Scale) will be completed, and subjects will then be housed overnight where they will be required to adhere to a standardized high-fat, high-sucrose diet;
 - Day 1: 1 dose of study drug will be administered at approximately 4:30pm followed by standardized ethanol consumption as outlined in the manual, and 1 dose of study drug will be administered at approximately 7 pm followed by continued standardized ethanol consumption to reach a target blood alcohol concentration (BAC) of 0.14 g/100 mL, measured via breathalyzer. For more details on the breathalyzer measurements, refer to the Study Procedures Manual. Symptom and sign assessments (with the exception of the CGI Improvement Scale) will be evaluated and should be completed as soon as practical after target BAC is reached. Study procedures will be reviewed for randomized subjects, and, based on the emerging data, the standardized ethanol solution and/or

BAC testing methods may be modified as needed to ensure target BAC is reached within a 4-hour window for the remaining subjects; and

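### The only visible statement of the inferential efficacy analysis names the comparison as AB versus BA sequence, whereas the model beside it estimates ADX-629 versus placebo; the contrast is wrongly named and should be corrected

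*Protocol*

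**What the plan says.** The Protocol synopsis, under Statistical Analyses, gives as its usual rule that the "comparison of change from baseline in endpoints over time between the 2 treatment sequences will be assessed by a mixed effect model" (a repeated-measures model). The next sentence gives the model for change from baseline: "sequence, period, timepoint, treatment, and the interaction of treatment by timepoint as fixed effects, and baseline as a covariate".

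The design is not in doubt. SAP 2.2.1 states: "This study will utilize a 2-sequence, 2-period, 2-way crossover design". Both documents define the sequences as AB and BA, with A as ADX-629 and B as placebo. Protocol 5.1 confirms that each subject takes both: "All subjects will receive 3 doses of ADX-629 600 mg", and three doses of placebo.

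No other visible text settles which contrast is the efficacy result:

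- Protocol 9.2.1 (Analysis of Efficacy) is blacked out apart from a sentence on descriptive summaries.
- SAP 3.4 lists endpoints and a set of factors, with no visible model statement or contrast.
- No code is visible under SAP Appendix A.
- SAP Section 5 lists one change from the protocol, on analysis populations. It does not touch this wording.

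**The concern.** In an AB/BA crossover the drug effect is the difference between treatments within subjects. The sequence main effect is a different quantity: it reflects differential carryover and chance differences between the two groups of subjects. The synopsis names the sequence comparison and then specifies a model whose only interaction is treatment by timepoint. A comparison of sequences over timepoints would need a sequence-by-timepoint term, and there is none. The two sentences do not describe the same analysis.

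If the first sentence were followed literally, a null AB-versus-BA result could be reported as absence of activity when it carries no information on activity. If neither sentence is treated as decisive, the reported coefficient is left open across a long list of symptom, sign and pharmacodynamic measures. The SAP also groups by sequence elsewhere: Section 3.5 summarizes safety data by treatment sequence and in total.

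**Working it through.** The plan gives no power, effect size, SD or significance level to reproduce. Protocol 9.2.5 says: "The sample size is not based on statistical considerations and is not formally powered as all endpoints are exploratory in nature".

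**Inputs from the documents.** AB/BA design. About 30 subjects (Protocol 9.2.5). Mean half-life 3.49 to 6.83 hours (Protocol 1.1.2). Washout of at least 14 days (Protocol 3.1), or 14 ± 2 days (SAP 2.2.1), so 12 days at the shortest. The two washout statements differ and need reconciling; this point does not turn on which applies.

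**1. Expected contrasts.** Let p1 and p2 be the period means, τ the ADX-629 minus placebo effect, and λ the differential carryover into Period 2.

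| Sequence | Period 1 | Period 2 |
|---|---|---|
| AB | p1 + τ | p2 + λ |
| BA | p1 | p2 + τ |

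- Sequence contrast: ½[(p1 + τ) + (p2 + λ)] − ½[p1 + (p2 + τ)] = λ/2
- Treatment contrast: ½{[(p1 + τ) − (p2 + λ)] − [p1 − (p2 + τ)]} = τ − λ/2

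With λ = 0, the sequence contrast is 0 for τ = 0, -5, -10 and -20, while the treatment contrast equals τ each time. With λ = -2, the sequence contrast is -1.0 for every τ.

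**2. Is λ near zero reasonable?** 14 days is 336 hours: 336/6.83 = 49 to 336/3.49 = 96 half-lives. 12 days is 288 hours: 288/6.83 = 42 to 288/3.49 = 83 half-lives. Pharmacokinetic carryover is negligible on either statement.

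**3. Missing Period 2 data.** If a share d of each sequence has no Period 2 data and raw sequence means are compared, the contrast is τd/(2 − d).

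- τ = -10, d = 10%: -10 × 0.1/1.9 = -0.53
- τ = -10, d = 20%: -10 × 0.2/1.8 = -1.11
- τ = -20, d = 20%: -20 × 0.2/1.8 = -2.22

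The contrast is then not exactly zero, but it recovers only a small fraction of the effect.

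**4. The synopsis model, simulated.** Assumed, not from the documents: 15 subjects per sequence, 4 timepoints, between-subject SD 10, within-subject period SD 8, residual SD 6, period effect 3, two-sided 0.05, complete data, no carryover, 200 runs per scenario.

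| True τ | Sequence coefficient, mean | Significant | Treatment coefficient, mean | Significant |
|---|---|---|---|---|
| 0 | -0.06 | 4.0% | -0.04 | 6.5% |
| -10 | -0.12 (Monte Carlo SE 0.31) | 5.5% | -10.01 | 97% |

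The same fitted model contains both coefficients, and only one of them responds to the drug.

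**5. AB versus BA within Period 1.** This alternative reading does estimate the drug effect, but between subjects. With between-subject variance sB² and within-subject variance sw², the variance ratio to the crossover contrast is [2(sB² + sw²)/15]/[2sw²/30] = 2/(1 − ICC). The ICC is not in the documents. At 0.3, 0.5 and 0.7 the ratio is 2/0.7 = 2.9, 2/0.5 = 4 and 2/0.3 = 6.7. At ICC 0.5 and a true effect of one within-subject SD, 6,000 simulated trials gave significance in 46.3% for Period 1 alone, 96.5% for the crossover contrast and 4.7% for the sequence contrast.

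**The case against.** The strongest reply is that this is a slip of wording. The model sentence follows immediately and contains "sequence, period, timepoint, treatment, and the interaction of treatment by timepoint as fixed effects". The only contrast over timepoints that it can give is the treatment contrast, so that is probably what is meant. There is also a valid reading: comparing the Period 1 to Period 2 change between the two sequences is the standard crossover treatment test, because treatment is the sequence-by-period contrast. On that reading the sentence is correct and fully efficient.

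Much of this stands. A reader might infer from the first sentence that the plan cannot detect or estimate an ADX-629 effect. The documents do not support that, because the specified model contains the needed terms and step 4 shows that it recovers the effect. The valid reading, however, has to be supplied by the reader. The sentence speaks of change from baseline over time, SAP 3.1.3 resets the efficacy baseline in each period, and the model's time factor is timepoint.

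Three further limits stand:

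- A reader might infer that this is the only inferential comparison in the plan. It is only the one that is visible. The SAP abbreviation list defines least squares and confidence interval, neither of which appears in the visible body, so withheld text may state the right estimates.
- The synopsis says the model applies in general. It cannot apply to every endpoint: the CGI-Improvement Scale is given only on Day 2 and has no Check-In baseline.
- The endpoints are exploratory and unpowered, which does not support treating this as a critical defect.

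**Conclusion.** Wrong as written; severity moderate to minor. The comparison named in the synopsis is AB versus BA. Its main-effect contrast has expectation λ/2, which is zero without differential carryover, for any drug effect. That result assumes complete data or, if data are missing, a model-adjusted rather than raw sequence mean. The washout makes a λ near zero reasonable on pharmacokinetic grounds.

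The model in the next sentence can estimate the drug effect, so the error lies in the named contrast and its conflict with the model. The algebra does not depend on assumed values; the 97%, 46.3% and 96.5% figures and the variance ratio do. Whether Protocol 9.2.1 or the SAS code already names the treatment contrast cannot be determined from the visible text. Even if it does, the synopsis sentence should agree with it.

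**What to change.** In the synopsis sentence, name the comparison as ADX-629 versus placebo in place of the two sequences. State that the reported estimates are the treatment least-squares mean differences with confidence intervals, overall and at each timepoint, the latter from the treatment-by-timepoint term. Keep sequence in the model as an adjustment term only, not as an efficacy result. Make any matching text in Protocol 9.2.1, SAP 3.4 and SAP Appendix A agree, and record the change in SAP Section 5 if it is made in the SAP rather than the protocol.

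The cost is a sentence or two in each document. It needs no additional data or subjects, and it should be done before database lock, when the SAP is due to be final.

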4.3 Withdrawal Criteria

Participation of a subject in this study may be discontinued for any of the following reasons:

- Sponsor decision;
- The subject withdraws consent or requests discontinuation from the study for any reason;
- Occurrence of any medical condition or circumstance that exposes the subject to substantial risk and/or does not allow the subject to adhere to the requirements of the protocol;
- Any serious AE (SAE), clinically significant AE, severe laboratory abnormality, intercurrent illness, or other medical condition that indicates to the Investigator that continued participation is not in the best interest of the subject;
- Pregnancy;
- Subject requirement of prohibited concomitant medication;
- Subject failure to comply with protocol requirements or study-related procedures; or
- Termination of the study by the Sponsor or the regulatory authority.

Unless a subject withdraws consent for further follow-up, subjects who discontinue study drug (ADX-629 or placebo) will continue in the study for acquisition of safety assessments through the follow-up telephone call. If a subject withdraws prematurely from the study due to the above criteria or any other reason, study staff should make every effort to complete the full panel of assessments scheduled for the Early Termination Visit. The reason for subject withdrawal must be documented in the electronic case report form (eCRF).

In the case of subjects lost to follow-up, attempts to contact the subject must be made and documented in the subject's medical records.

Withdrawn subjects may be replaced at the discretion of the Sponsor.

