5.2 Rationale for Dosing

5.3 Randomization and Blinding

Subjects will be randomized to 1 of 2 treatment sequences (AB or BA) on Day 1 of Treatment Period 1.

- Treatment A: 3 oral doses of ADX-629 600 mg (2×300 mg) oral tablets; and
- Treatment B: 3 oral doses of matching placebo.

Subjects, Investigators, and study site personnel (including the Sponsor/designee) involved in the administration and assessment of the study drug will be blinded to the subject treatment assignments throughout the study.

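### The synopsis model lets the treatment effect vary by timepoint but holds the period effect constant across timepoints; adding period-by-timepoint is a cheap, minor improvement

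*Protocol*

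**What the plan says.** The SAP (2.2.1) states the design: "This study will utilize a 2-sequence, 2-period, 2-way crossover design". Protocol 5.3 adds: "Subjects will be randomized to 1 of 2 treatment sequences (AB or BA) on Day 1 of Treatment Period 1". No allocation ratio or blocking is visible.

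The only full list of model terms that can be read is in the Protocol synopsis, under Statistical Analyses. Change from baseline is analysed by a mixed model for repeated measures "with sequence, period, timepoint, treatment, and the interaction of treatment by timepoint as fixed effects, and baseline as a covariate". Period is a main effect only, and no covariance structure is visible.

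Most symptom and sign measures have four post-baseline readings per period. The Day 1 set "should be completed as soon as practical after target BAC is reached", and the Day 2 sets fall at about 7 am, 10 am and 1 pm. Pharmacodynamic (PD) markers have two post-baseline samples per period (Protocol 7.3). The symptom and sign baseline is taken at Check-In, before any ethanol, and SAP 3.1.3 makes the efficacy baseline period-specific.

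The other places where a model would appear are incomplete. Protocol 9.2.1 is blacked out. SAP 3.4 shows a list of factors (timepoint, baseline, BAC, drinks, two emesis variables) without treatment, period or sequence, so it cannot be the whole model. The code in SAP Appendix A is not shown. SAP section 5 lists one change from the protocol, on analysis populations.

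**The concern.** In an AB/BA crossover, the treatment contrast at a timepoint comes from the within-subject period differences at that timepoint, corrected for the period shift at that timepoint. The stated model corrects every timepoint by one common shift. If the true shift varies, the correction is wrong at each timepoint by the gap between its own shift and the common one.

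A varying shift is plausible here. One reading is taken at a target BAC of 0.14 g/100 mL and three on the following day. Practice on timed balance and heel-to-toe tests, or a second exposure to the challenge, could act differently in those two states. The period-specific baseline is taken sober, so subtracting it cannot remove a shift that appears only under intoxication.

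The ADX-629 minus placebo contrasts by timepoint are what the treatment-by-timepoint term is there to provide. At stake are the width of their intervals and, when sequences are unequal, their values.

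**Working it through.** **Inputs from the documents.** The plan's one relevant figure is its size: "Approximately 30 subjects are expected to be enrolled in the study". It cannot be re-derived, because "The sample size is not based on statistical considerations and is not formally powered as all endpoints are exploratory in nature". The number of post-baseline timepoints T is 4 for most symptoms and signs and 2 for PD markers.

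**Assumptions not in the documents.** 30 completers; within-subject period differences with SD 1 at each timepoint; an extra period shift of d SD at one timepoint only; no missing data; no baseline covariate.

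**Algebra.** Let D_ik be subject i's Period 1 minus Period 2 difference at timepoint k:

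D_ik = π_k + s_i τ_k + e_ik, with s_i = +1 for AB and −1 for BA.

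The stated model replaces every π_k by a common π. With timepoints weighted equally, the estimate of π is about d/T. The uncorrected remainder is then (1 − 1/T)d at the shifted timepoint and −d/T at each other timepoint.

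*Equal sequences.* The remainder cancels from the contrast but stays in the residual variance.

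- Unstructured covariance: SE ratio at the shifted timepoint ≈ √(1 + ((1 − 1/T)d)²).
- Compound symmetry, T = 4: the squared remainders are averaged over timepoints, (0.75² + 3 × 0.25²)/4 = 0.1875, so the SE ratio ≈ √(1 + 0.1875d²) at every timepoint.

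| Shift d | T = 4, unstructured | T = 4, compound symmetry | T = 2 |
|---|---|---|---|
| 0.25 | √(1 + 0.1875²) = 1.02 | √1.0117 = 1.01 | √(1 + 0.125²) = 1.01 |
| 0.5 | √(1 + 0.375²) = 1.07 | √1.0469 = 1.02 | √(1 + 0.25²) = 1.03 |
| 1.0 | √(1 + 0.75²) = 1.25 | √1.1875 = 1.09 | √(1 + 0.5²) = 1.12 |

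*Unequal sequences.* Bias at timepoint k ≈ ((n_AB − n_BA)/n) × remainder at k. For an assumed 18/12 split with T = 4, the imbalance is (18 − 12)/30 = 0.2:

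- d = 0.5: 0.2 × 0.75 × 0.5 = 0.075 SD at the shifted timepoint, and −0.2 × 0.25 × 0.5 = −0.025 SD at each of the others.
- d = 1.0: 0.15 SD and −0.05 SD.

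The standard error is widened in this case too, so both faults occur together.

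**Simulation.** Data of this form were fitted by iterated generalised least squares, with and without period-by-timepoint (correlation between timepoints 0.3 or 0.6, 400 runs per setting).

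- 15/15, T = 4, unstructured: model SE 0.195 at d = 0.5 and 0.23 at d = 1.0, against a correct value of 1/√30 ≈ 0.18. That is about 8% and 27 to 28% too wide, with bias about 0. Coverage at d = 1.0 was about 99%. The excess over the closed form is expected: the inflated variance lowers the weight of the shifted timepoint in the common period estimate and leaves a larger remainder.
- 15/15, d = 1.0: about 9 to 10% too wide at all four timepoints under compound symmetry, and about 12 to 13% at both timepoints with T = 2.
- 19/11, T = 4, d = 1.0: bias about 0.19 to 0.22 SD, with coverage down to 86 to 91%. The closed form gives (8/30) × 0.75 = 0.20.
- With period-by-timepoint added: bias within ±0.02 SD in every setting, and model SE in line with the empirical SD. With no shift, the SE stayed at about 0.18.

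**The case against.** **The operative model may not be the synopsis model.** The synopsis sentence is a general statement, the protocol lets the SAP supersede it, and the fuller descriptions are redacted or not shown. A reader might infer that the planned analysis definitely omits the term. The documents do not support that: the point applies to the model as visibly stated.

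**The ethanol procedure.** A reader might take the provision that "the standardized ethanol solution and/or BAC testing methods may be modified as needed to ensure target BAC is reached" as proof of a period shift. It is not. The sentence goes on to limit the change to subjects still to come, so it is a calendar-time change. Only a subject whose two periods straddle it would have a resulting Period 1 to Period 2 shift, and the number of such subjects is not given. Both periods also aim at the same BAC, and the SAP's BAC and drinks factors may absorb some exposure differences. They would not absorb practice.

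**The shift and the imbalance are assumed.** Both are. Practice would not affect photographs or PD markers, and CGI-Improvement is collected only on Day 2, so a Day 1 shift cannot arise for it. The 18/12 split is illustrative. Reserve subjects are admitted to fill the sequences, and "Withdrawn subjects may be replaced at the discretion of the Sponsor". These provisions make a large imbalance less likely but do not guarantee balance. Simple 1:1 randomisation of 30 subjects, also an assumption, would give unequal sequences with probability 0.86.

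**A period main effect is a legitimate, parsimonious choice in an unpowered study.** This stands as a reason for low severity. With equal sequences the error is conservative.

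**Conclusion.** The point holds for the synopsis model as written: treatment may vary by timepoint and period may not. The consequence depends on a shift of unknown size. The widening of standard errors is negligible at 0.25 SD (about 2%), modest at 0.5 SD (about 8% unstructured, 2 to 3% otherwise) and material only near 1.0 SD (about 27% unstructured, 9 to 13% otherwise). Bias needs both a varying shift and unequal completers.

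A reader might infer that treatment estimates are biased in general, that the harm stays at one timepoint, or that the trial loses a stated amount of power. None of these follows. Equal sequences give no bias. Compound symmetry, or only two timepoints, spreads the widening to all timepoints, and imbalance puts a small opposite bias on the others. The plan sets no alpha, effect or power target to lose against.

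This is a cheap improvement of minor severity, since all endpoints are exploratory.

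**What to change.** Add period-by-timepoint to the fixed effects in the Protocol synopsis, SAP 3.4 and the sample code, giving sequence, period, timepoint, treatment, treatment-by-timepoint, period-by-timepoint and baseline. Report the ADX-629 minus placebo contrast at each timepoint from that model. If the redacted Protocol 9.2.1 or the SAP text not shown already contains the term, only the synopsis needs aligning. State the covariance structure as well, because the size of the effect depends on it.

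The cost is T − 1 fixed-effect degrees of freedom: 3 for measures with four readings and 1 for PD markers. No extra subjects, visits or data are needed, and with no varying shift the simulations showed no measurable loss of precision.
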